**Potential solution:** To develop of chronic condition activated self-management skills, we designed and pilot tested a peer-based coaching intervention - ***Peer i-Coaching for Activated Self-Management Optimization (PICASO)*** - for AYAs with childhood onset chronic conditions. This novel, mobile health intervention utilizes an established telephone/text based secure interface to allow AYAs access knowledge, experience, and instrumental/emotional support from a trained peer coach who has already developed independence an active self-manager. Peers with shared experiences provide instrumental (e.g., health maintenance skills) and emotional support that likely lead to improvements in quality of life. Involving peers in supporting AYAs with chronic conditions to promote self-management and patient activation disrupts the typical over-reliance on the parent and health care provider that often impedes developing independence. Thus, we propose a five-year randomized controlled trial that will include 225 AYAs (16-22 years) with childhood onset chronic conditions to address these **specific aims**:

**Aim 1:** Determine the efficacy of PICASO on primary outcomes (self-management, patient activation) and secondary outcomes (transition readiness, health-related quality of life, emotional health) across 12 months.

**Hypothesis:** Compared to an attention control group, the PICASO group will report greater improvement in primary and secondary outcomes.

**Aim 2:** Explore age, sex, race/ethnicity, chronic condition, and disease severity as moderators of trajectory of PICASO effects on self-management, patient activation, transition readiness, health-related quality of life and emotional health. **Approach:** Explore the moderating effects of patient characteristics on PICASO outcomes.

**Aim 3:** Explore mechanisms of PICASO impact by describing AYA experiences with the intervention to characterize how they may be related to intervention components and contexts, with the goal of understanding intervention mediators and barriers to future large-scale implementation. **Approach:** Using mixed methods, qualitative interview data will be integrated with quantitative coaching data (e.g., coach/participant alliance).

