Secondary outcome assessments. The following constructs will be assessed as secondary outcomes at baseline, 3-, 6-, 9-, and 12-months post randomization: (a) transition readiness, (b) health related quality of life, and (c) emotional health. Transition readiness will be measured by the Transition Readiness Assessment Questionnaire (TRAQ). The TRAQ assesses transition readiness in youth with COCC in domains of self-advocacy (communication and use of resources in the community and school) and chronic disease self-management (scheduling appointments, asking questions of health care providers, filling prescriptions). Health related quality of life will be measured using the Short-Form 12 (SF-12) which produces weighted subscales on physical and mental components of quality of life. Emotional health will be measured using the Brief Symptom Inventory (BSI) which assesses emotional symptom experience (depression, anxiety, somatization) over the previous week.

**3.D.3.e. Data management plan for all aims.** [Human Subjects and Clinical Trials Information Sections 3.1.b. & 3.3.3](#) detail data management and security. Briefly, all study data will be entered by participants and the

study Clinical Research Coordinator (CRC) via REDCap data system residing on a Duke University RHEL Server. Leveraging a unique password system, only the Study Manager will be unblinded to study group in the data system. Weekly reports will be reviewed to monitor enrollment, retention, safety, and missing data.

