#### Aim 1 and 2 Analysis Plan

Descriptive statistics will be used to detail the sample characteristics of the (a) coaches and randomized AYAs and (b) detail the study outcomes for the AYAs at the five-assessment point (baseline, 3-, 6-, 9-, 12-months post randomization). Non-directional statistical tests will be performed, with the significance level set at 0.05 for each test. The significance level will not be adjusted for multiple outcomes and tests (see Power section below). Estimated effect sizes and their 95% confidence intervals (CI) will be reported to address magnitude of effect and clinical significance for the efficacy and moderator analyses (Aims 1 and 2, respectively).

**AYA Sample Characteristics.** Chi-square/Fisher's Exact Tests for categorical variables and General Linear Models (GLM) for continuous measures will be used to test for group (PICASO vs attention control) differences in the baseline demographic and clinical characteristics as well as baseline outcome measures for the AYAs. A GLM approach, which calculates least square means to adjust for unequal sample sizes, will be used to test for between-group differences in the means for continuous measures. Any significant between-group difference in a baseline characteristic detected will be evaluated as a potential covariate in the efficacy analyses

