**Aim 2 Moderator Analyses.** To explore whether age, biological sex, race/ethnicity, chronic condition, and/or disease severity moderate the trajectory of PICASO effects on the primary and secondary outcomes, the trajectory analysis approach described in Aim 1 will be used to evaluate the moderating effects of each candidate moderator on each outcome. Each candidate moderator will be evaluated separately by incorporating the variable (e.g., age) and its interaction with group and time as fixed effects in the model for each outcome. By definition, a significant candidate moderator-by-group-by-time interaction would indicate that the variable moderates the effects of the PICASO compared to the control group over time. If a moderator interaction is significant at the 0.05 level, the RRM core model applied in Aim 1 will be fitted for subgroups of the moderator to better determine the differential trajectory of change from baseline to 12-month within each moderator subgroup. This analytic method will be applied in accordance with recommended approaches for assessing moderator effects in trajectory and/or growth models.

**Aim 3:** Explore mechanisms of PICASO impact by describing AYA experiences with the intervention and the InquisitHealth Mentor 1:1™ Web Based Portal. Aim 3's goal is to understand intervention mediators by characterizing how intervention components, as well as the unique case context of their use, may (a) target (or miss) within-case needs, (b) address variability across chronic condition and age contexts, and (c) impact patterns in outcome measures. **Approach & goal:** We will integrate findings from qualitative interviews with AYA outcomes. This mixed methods analysis will provide insight into intervention mediators (mechanisms of action) and highlight how outcomes may be related to unique case contexts; both of which will lead to future intervention optimization through enhanced personalization, replicability, and scalability.

**Aim 3 Mixed Methods Analyses.** We will explore AYA experiences with the PICASO using a mixed methods approach to characterize participants' experiences with the intervention to understand mechanisms of action, how outcomes may be related to unique case contexts, and if barriers to broader implementation and dissemination are perceived. This knowledge will also guide future intervention optimization through enhanced

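### Aim 2 follows up significant moderators by subgroup refits, which forces an unstated cut of age and gives level-specific effects only where p<0.05

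*Combined protocol and SAP*

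**What the plan says.** The Aim 2 Moderator Analyses paragraph of the Aim 1 and 2 Analysis Plan lists five candidates: "age, biological sex, race/ethnicity, chronic condition, and/or disease severity". The test is set up one moderator at a time: "Each candidate moderator will be evaluated separately by incorporating the variable (e.g., age) and its interaction with group and time as fixed effects". A significant moderator-by-group-by-time term is taken to show moderation. Only then does the next step apply: "the RRM core model applied in Aim 1 will be fitted for subgroups of the moderator". The plan does not say whether age enters as continuous or grouped, and it gives no cut-points for age or severity.

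The opening of the same Analysis Plan fixes the error rate, "with the significance level set at 0.05 for each test", and adds: "The significance level will not be adjusted for multiple outcomes and tests". It also promises effect sizes with 95% confidence intervals for both the efficacy and the moderator analyses. Section 2 and Table 3 label Aim 2 exploratory. Section 3.C.8 gives power for Aim 1 only, yet says that the sample will support dependable moderator effect sizes. No calculation is given for that statement.

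**The concern.** There are two separate issues.

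The first concerns age, and disease severity if it is a continuous score. The three-way interaction model already yields the PICASO-control difference at any age. Refitting the Aim 1 model in subgroups of age discards that and needs a cut. The cut could be chosen after the data are seen, the estimates are less precise, and the reported effects may disagree with the test that triggered them.

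The second concerns which results are shown. The only level-specific analysis described is the refit, and it is conditional on p<0.05. When power for interactions is low, estimates that pass such a filter are too large on average. The protocol says coaching can be tailored to younger participants, and it names a multi-site trial as the next step. An inflated or chance age effect could therefore shape later work. No Aim 1 conclusion is affected.

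**Working it through.** **Inputs from the documents.** Two-sided 0.05 per test, unadjusted (Aim 1 and 2 Analysis Plan). Five moderators (Aim 2 Moderator Analyses). Five outcome constructs, two primary and three secondary (Section 2). 150 PICASO and 75 control, d = 0.50, attrition up to 20%, so 120 and 60 at worst (3.C.8). Age 16 to 22 (Table 6). Smallest condition category 30 and 15 (Table 5).

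**Assumptions.** Outcome SD of 1. Complete, balanced data, so that participants' own slopes stand in for the random-coefficients model. Ages uniform from 16 to just under 23. Binary moderators evenly split. Chronic condition counted as one test per outcome.

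1. *The plan's own figure.* The two-mean formula gives control n = 1.5 × (1.96 + 0.842)² / 0.5² = 47.1, rounded up to 48. The total is then 144, or 144/0.8 = 180 after attrition, not 225. Power at d = 0.50 is 94% with 150:75 and 89% with 120:60, so the stated minimum of 80% is met. The correlation inputs to the sample-size software are not given, so the gap to 225 is not shown to be an error. There is no interaction power figure to reproduce.

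2. *Age, continuous against split.* Scale age so that its whole range has length 1; its variance is then 1/12. The group-by-age coefficient has variance (1/150 + 1/75) × 12 = 0.24. The contrast between the mean ages of the two halves is half that coefficient, with variance 0.06 and SE 0.245. After a midpoint split, each half has 75 PICASO and 37.5 control, so the variance is 2 × (1/75 + 1/37.5) = 0.08 and the SE is 0.283. The ratio is 0.08/0.06 = 1.33, so the split keeps 75% of the information. A simulation of 6,000 trials per setting gave SEs of 0.247 and 0.285. For a true contrast of 0.5 SD, power was 53% continuous against 41% split at N=225, and 43% against 33% at N=180.

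3. *Categorical moderators.* In the same simulation with a two-level moderator, separate fits and one joint interaction model gave the same contrast (difference below 1e-14) and the same mean SE of 0.285. In the 30:15 category the half-width is 1.96 × √(1/30 + 1/15) = 0.62 SD, or 0.69 SD with 24:12. That width reflects how few participants there are, and the joint model gives essentially the same.

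4. *The p<0.05 filter.* For an even-split interaction, SE = √(2/75 + 2/37.5) = 0.283 at N=225 and √(2/60 + 2/30) = 0.316 at N=180. The exaggeration column is the average overstatement among significant results.

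| True interaction | Power, N=225 / 180 | Exaggeration, N=225 / 180 |
|---|---|---|
| 0.50 SD | 42% / 35% | 1.5 / 1.7 times |
| 0.25 SD | 14% / 12% | 2.8 / 3.1 times |

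An estimate must reach 1.96 × SE = 0.55 or 0.62 SD to be significant, which exceeds the whole planned main effect of 0.50. With no true interaction, a significant estimate averages about 2.34 × SE = 0.66 or 0.74 SD in absolute size. To locate the cause: with a true age contrast of 0.25 SD, N=225 and a significant continuous-age test, the mean absolute estimate was 0.62 from the continuous model and 0.61 from the subgroup fits. The filter causes the exaggeration, not the refit.

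5. *Number of tests.* 5 × 5 = 25 tests, so 25 × 0.05 = 1.25 false positives are expected if no moderator is real, whatever the correlation between tests. The chance of at least one is 1 − 0.95²⁵ = 72% if tests are independent. With outcomes correlated 0.3, 0.5, 0.7 or 0.9 (assumed) it is 69%, 63%, 55% or 41%. Section 3.D.3.d says the SF-12 yields "weighted subscales on physical and mental components of quality of life"; if both are analysed there are 30 tests and 1.5 expected.

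**The case against.** Aim 2 is exploratory throughout: Section 2 gives Aim 1 a hypothesis and Aim 2 only an approach. The decision rests on a formal interaction test, which avoids the common error of comparing subgroup p-values. The lack of adjustment is disclosed, and the commitment to confidence intervals carries no significance condition. The plan never says that age will be cut, and if age is continuous in the test, a later cut does not change which moderators are declared.

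Much of this stands. Exploratory status makes multiplicity adjustment a matter of judgement, and the interaction test is sound. But a model cannot be fitted within subgroups of age without grouping age, and the general promise of intervals does not say that effects at each moderator level will be shown when the interaction is not significant.

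A reader might infer more than the documents support:

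- *That subgroup refitting loses precision for every moderator.* For sex, race/ethnicity and condition category it does not; only the pooling of variance components is lost.
- *That refitting causes the exaggeration.* A joint model with the same filter shows it equally.
- *That a false moderator is more likely than not.* The 72% assumes independent tests and no real moderator, and it falls to 41% at an outcome correlation of 0.9.
- *That most declared moderators would be false.* This depends on how many are real, which the documents do not give. With 10% to 50% real and power of 14% to 42% (both assumed), the false share runs from 11% to 76%.

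**Conclusion.** The concern holds in limited form. For age, and for severity if continuous, the planned follow-up needs an unstated cut and gives estimates with about 1.33 times the variance of those available from the interaction model. This figure assumes roughly uniform ages and a midpoint split. For the categorical moderators the refit is harmless to precision. Restricting level-specific effects to interactions with p<0.05 selects inflated estimates: about 1.5 to 1.7 times for a true 0.5 SD even-split interaction, and about 3 times for 0.25 SD. The expected 1.25 false positives in 25 tests applies only if no moderator is real. All figures treat participant slopes with SD 1 as a stand-in for the mixed model. Because Aim 2 is exploratory, the case is for better estimation and full reporting; the documents do not make error-rate control obligatory.

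**What to change.** Replace the subgroup refits with contrasts from the single three-way interaction model:

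- Keep age continuous, and severity too if it is a continuous score.
- Report the PICASO-control difference at 12 months with a 95% CI at pre-set ages (for example 16, 18, 20 and 22), at pre-set severity values if continuous, and at each level of the categorical moderators.
- Do this for all five moderators and all outcomes, whatever the interaction p-value.
- State how many interaction tests are made and label the results hypothesis-generating. False-discovery-rate control is optional.

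The cost is SAP wording and a longer results table; no new data and no new model are needed. The method assumes a functional form for age, which can be checked by adding a non-linear term.

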### **3.C.8. Sample Size and Power Considerations**

A target sample size of 225 AYAs (PICASO: N=150; control: N=75) will be provide at least 80% statistical power to address the efficacy of PICASO compared to the attention control condition (Aim 1) and will provide sufficient heterogeneity to obtain reliable estimates of effect sizes for the exploratory moderator analyses. Using PASS software (NCSS LLC, Kaysville, UT), the sample size determination for the two primary outcomes was based on the following assumptions: (a) mixed-effects trajectory analyses using RRMs; (b) two-tailed tests with significance set at 0.05 per test; and (c) medium effects (Cohen  $d$  equivalent of 0.50); and (d) unstructured within-subjects correlation patterns over time. The significance level of 0.05 will not be adjusted for evaluating two primary outcomes. Although the mixed-effects models allow for data missing at random, the sample size of 225 takes into account an attrition rate of up to 20% over time, and thus, should provide 80% power for both the ITT and completers' analyses of the two primary outcomes.

### **3.C.9. Methodological Considerations Relevant to a Robust, Unbiased, Reproducible Approach.**

**Intervention:** Peer coaches will receive an initial five-day training on the process of coaching, which includes didactic sessions on the stages of coaching, motivational interviewing skill development, and opportunities to practice coaching skills. Practice sessions are observed by the coach supervisor, who developed the peer coaching curriculum, and feedback is provided in order to assess intervention fidelity. In addition, coaches receive ongoing, semi-monthly group supervision to provide ongoing training on the peer coaching process, facilitate additional practice sessions to advance skill development, troubleshoot coaching challenges, and maintain intervention fidelity. The coach supervisor also provide individual supervision as needed for coaches experiencing difficulties with the coaching process. During these sessions, the peer coach role plays a scenario that they may encounter with their participants with the supervisor in the role of the AYA. After the 10-minute practice, the supervisor and coach review the interaction and provide feedback on strengths and areas for improvement in order to implement coaching with fidelity.

**Generalizability:** We believe that the external validity of the proposed PICASO trial is very high. First, our approach to sampling using a modified noncategorical approach with a broad list of COCCs (sickle cell disease, chronic kidney disease, systemic lupus erythematosus, type 1 diabetes, inflammatory bowel disease, severe asthma, stem cell transplantation, organ transplantation, and childhood cancer survivor, increases the likelihood that the results will be applicable across conditions most often experiencing self-management challenges during the critical window of transition. Our focus on outcomes that are not generally found to have disease-specific ramifications, also strengthens the external validity of the potential findings.

**Replicability** is an intervention strength. **Technology:** As described in Innovation, replicability and scalability across future sites is ensured by the ability of InquisitHealth Mentor 1:1™ Web Based Portal to capture data directly from coaching sessions. Our multidisciplinary research team assists in protecting against bias that may be inserted by virtue of disciplinary lenses.

### 3.C.10. Timeline

See Human Subjects and Clinical Trials Information Section 4.2.a.13 for detailed description of timeline.

	Year 1				Year 2				Year 3				Year 4				Year 5			
	1	2	3	4	1	2	3	4	1	2	3	4	1	2	3	4	1	2	3	4
Specific timeline																				
Aims 1 & 2: RCT																				
Subcontracts finalized with programmers	X																			
Web app finalized	X																			
Digital case report forms (ePRO) final	X	X																		
DSMB formation & charter	X	X																		
Regulatory documentation: IRB approval, human subjects training	X	X																		
Registration on ClinicalTrials.gov			X																	
Staff training		X	X																	
Peer Coach Recruitment & Hiring	X	X																		
Investigator / team meetings	X	X	X	X	X	X	X	X	X	X	X	X	X	X	X	X	X	X	X	X
Aim 1 randomization & all subject assessments																				
0-25% (n=62 cumulative)		X	X	X	X															
26-50% (n=125 cumulative)						X	X	X	X											
51-75% (n=187 cumulative)										X	X	X	X							
76-100% (n=225 cumulative)														X	X					
Data collection complete																		X		
Data cleaning	X	X	X	X	X	X	X	X	X	X	X	X	X	X	X	X	X	X	X	
Database lock																		X		
Statistical analyses																			X	
Submit primary manuscript																				X
Progress reports to NIH		X				X				X				X		X				X
Data to DSMB; DSMB mtgs.	X		X			X			X		X			X		X		X		X
Update ClinicalTrials.gov	X		X		X		X		X		X		X		X		X		X	
Submit grant application for multi-center pragmatic trial																				X
Aim 3: Participant experiences																				
Aim 3 accrual & subject assessments					X	X	X	X	X	X	X	X	X	X	X	X	X	X	X	
Aim 3 data analysis							X				X			X			X	X	X	

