**Table 6. Overview of eligibility criteria**

Inclusion
1. AYA 16 to 22 years
2. Childhood onset chronic condition from 1 of 3 condition categories (see Table Y).
3. Read and speaks English
4. Access to internet via computer or Smart Phone
4. Access to telephone (Smart Phone not required as text feature can be accessed via internet)
Exclusion
1. Diagnosed cognitive dysfunction
2. Need for English translator

**3.D.3.d. Outcome measures.** Study outcomes are described in detail in [Human Subjects and Clinical Trials Information Section 4.3](#). All outcomes have been piloted by our team and chosen based on the conceptual model, expert recommendations, and psychometrics. Response burden will be minimized with short instruments and online data entry via REDCap survey. Pilot testing confirmed completion times ranging from 15-20 minutes.

Primary outcome measures. The constructs of (a) self-management and (b) patient activation will be assessed at baseline, 3-, 6-, 9-, and 12-months post randomization. Self-management will be measured using the Partners in Health Scale (PIH), assessing chronic condition self-management knowledge, partnership in treatment, recognition and management of symptoms, and coping. Patient activation will be measured using the Patient Activation Measure (PAM). The PAM measures patient activation through self-reports of knowledge, skills, and confidence related to self-management of one's own health care.

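### Data collection and database lock are scheduled for Year 5 Q2, but participants randomised in Year 4 Q3 are due for their 12-month primary assessment in Year 5 Q3

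*Combined protocol and SAP*

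**What the plan says.** The chart in Section 3.C.10 divides five years into 20 quarters. Under the heading "Aim 1 randomization & all subject assessments" it gives four cumulative accrual rows. The third, "51-75% (n=187 cumulative", ends in Year 4 Q1. The fourth, "76-100% (n=225 cumulative", is marked in Year 4 Q2 and Q3. Both "Data collection complete" and "Database lock" are marked once, in Year 5 Q2. The statistical analysis follows in Year 5 Q3 and the primary manuscript in Year 5 Q4.

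Section 3.D.3.d places the primary outcomes (Partners in Health Scale, Patient Activation Measure) at "baseline, 3-, 6-, 9-, and 12-months post randomization". Section 3.D.4.a defines the primary outcomes as the scores after the intervention, which lasts 12 months. The Aim 1 efficacy analysis fits a random-coefficients model to all five assessments in everyone randomised, with a supplementary analysis of those who complete month 12.

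Section 3.C.10 refers the reader to Human Subjects and Clinical Trials Information Section 4.2.a.13 for the detailed timeline. That section is not among the documents available.

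**The concern.** Follow-up is counted from each participant's own randomisation, whereas the lock is a fixed calendar milestone. The lock therefore has to come at least 12 months after the last randomisation, and the chart leaves fewer than four quarters between the end of accrual and the lock.

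If the chart were followed, the latest entrants would have no month-12 value. That value is the post-intervention score, the end of the modelled trajectory and the condition for entering the completers' set. These participants would be missing because of the schedule, not because they left. The attrition allowance of up to 20% in Section 3.C.8 does not describe a loss of this kind.

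**Working it through.** **1. Quarter positions.** Each row of the chart has 20 quarter cells, so the marks can be counted without ambiguity.

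- Accrual rows: quarters 2–5, 6–9, 10–13 and 14–15. They are contiguous, so a shifted cell does not explain the result.
- Data collection complete, and lock: quarter 18 (Year 5 Q2, study months 51–54).
- Analysis: quarter 19. Manuscript: quarter 20.

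**2. Last 12-month visit.** Last randomisation quarter + 4 = 15 + 4 = 19, which is Year 5 Q3. In months, entry at 42–45 plus 12 gives 54–57, against a lock at 51–54. For the very last entrant the shortfall is 57 − 54 = 3 months if the lock is on the last day of its quarter, and 57 − 51 = 6 months if it is on the first.

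**3. Number affected.** The last block holds 225 − 187 = 38 participants over two quarters. Assuming even accrual, 38/2 = 19 enter in Year 4 Q3, and 19/225 = 8.4%.

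- Low end: a few, if most of the block enters in Year 4 Q2 and the lock comes late in its quarter.
- High end: 38, if the lock comes at the start of Year 5 Q2, because Year 4 Q2 entrants (months 39–42) are themselves due at months 51–54. A lock that early would also precede month 9 for the Year 4 Q3 entrants, which falls in the same window.

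**4. Month-12 two-group comparison (approximation).** Inputs from Section 3.C.8: 2:1 allocation, d = 0.50, two-sided 0.05, 20% attrition. Power comes from the noncentral t distribution with N − 2 degrees of freedom and noncentrality d × √(n₁n₂/N), which is 0.5 × √(2N/9) at 2:1.

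- The plan's own case: N = 225 × 0.8 = 180, noncentrality 3.16, power 88.2%. This agrees with the stated level of at least 80%.
- 19 also lost: N = (225 − 19) × 0.8 = 164.8, noncentrality 3.03, power 85.3%.
- 38 also lost: N = (225 − 38) × 0.8 = 149.6, noncentrality 2.88, power 81.7%.

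**5. Planned trajectory model.** With a lock at the end of Year 5 Q2, the Year 4 Q3 entrants still contribute baseline and months 3, 6 and 9. The plan gives no variance components. I therefore assumed a random-intercept share of baseline variance of 0.3–0.7 and a slope variance of 0.05–0.5 (baseline variance 1, time in years), with 19 × 0.8 = 15.2 retained participants missing only month 12. The information on the group-by-time slope falls by the equivalent of about 5–7 of 180 participants, compared with 15.2 if they were dropped altogether. Power falls by about 0.2 to 1.5 points. Starting from 88.2%, it ends at about 87%.

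**The case against.** The strongest reply is that this is a quarter-level grant-planning chart and not a data cut-off rule. Section 3.D.3.d commits to a 12-month assessment, the analysis plan includes everyone randomised, and nothing says that follow-up stops at lock. In practice the lock would probably slip by a quarter. The unavailable detailed timeline may already say so. All of this stands, and it limits the point to a schedule that needs correcting. It does not make the chart consistent, and no available section says that the lock waits for the last 12-month visit.

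A second reply is that the heading over the accrual rows covers assessments as well as randomisation, so the blocks might already include follow-up. That reading fails: the last block spans six months and cannot hold a 12-month follow-up.

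Two stronger inferences are tempting and are not supported:

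- **That the trial becomes underpowered.** A month-12 two-group test discards the earlier visits that the planned model uses, and even that test stays above 80% at the planned attrition. A loss fixed by calendar date is also compatible with the missing-at-random assumption. Some of the variance settings tried in the trajectory model give less than 80% before any loss, but that reflects the assumed variances and not the lock. In no setting tried does losing month 12 for 19 participants take power from above 80% to below it.
- **That other rows independently prove the lock date wrong.** "Data cleaning" does run to Year 5 Q3, but it starts in Year 1 Q1, before anyone is randomised, so it looks like a generic bar. "Aim 3 accrual & subject assessments" also runs to Year 5 Q3, but it starts in Year 2 Q1, before anyone could have finished a 12-month intervention, and nothing requires those interviews to precede the trial lock. Both rows are weak support.

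The figure of 19 is also fragile. It needs even accrual, and it takes the cumulative counts at face value. The counts 62, 125 and 187 are 24.8%, 50% and 74.8% of 250, but 27.6%, 55.6% and 83.1% of 225, so those rows may have been drawn up for another total.

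**Conclusion.** The concern holds as a scheduling error with modest consequences. On the chart as written, the Year 4 Q3 entrants are due for their last primary assessment after the database is locked, wherever in Year 5 Q2 the lock falls. About 19 of 225 (8.4%) would lack month-12 data under even accrual, with a range from a few to 38, and they would be shut out of the completers' set even if they stayed in the study.

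The power cost is about one point in the planned model under assumed variance components, or 88% to 85% in the simple comparison. From that starting level both stay above the stated 80%. The reason to act is that primary-endpoint data would be lost for no scientific reason. The conclusion rests on reading the four rows as dates of randomisation, and on the unavailable detailed timeline not already correcting the dates.

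**What to change.** Move the data-collection and lock milestones in Section 3.C.10 to the end of Year 5 Q3 or later, and place the final analysis and manuscript in Year 5 Q4. Add a rule that the database is not locked until the 12-month assessment window of the last randomised participant has closed, so that slower accrual moves the lock with it. Reconcile the chart with Human Subjects and Clinical Trials Information Section 4.2.a.13, and check the cumulative accrual counts against the target of 225 at the same time.

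The cost is about one quarter less for analysis and writing. No extra participants or visits are needed.

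Ending randomisation by Year 4 Q2 instead is not a cheap alternative. It would need all 38 remaining participants in one quarter, against about 15.5 per quarter in the earlier blocks (for example, 62/4 = 15.5). It would also leave the last visits in the lock quarter itself.
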